The following patient and perioperative data were collected and retrospectively analysed: patient age, body mass index (BMI), parity, history of vaginal delivery, previous pelvic surgery, type of surgery, total operating time, serum haemoglobin (Hb) drop (change between the preoperative Hb and postoperative Hb one day after surgery), (peri-) operative complications, postoperative pain score and size of the adnexal mass. The duration of surgery was defined as the time from the start of colpotomy to the end of vaginal closure. Bowel, bladder, ureteral or vascular injuries, as well as blood loss $>$ 300 ml, were considered as intraoperative complications. Short-term postoperative complications were classified as urinary tract infection, postoperative ileus, vaginal vault bleeding or infection, or haematuria. Postoperative pain was assessed using the visual analogue pain scale (VAS) (scoring from 0 = no pain to 10 = worst imaginable pain). The VAS score was evaluated at 6 and 24 hours postoperatively. All women received the same intraoperative analgesia: intravenous

paracetamol 1000 mg and ketorolac trometamol 20 mg. Postoperative pain was managed by paracetamol 1000 mg and ketorolac trometamol was administered on patient's demand. No bowel preparation was done prior to surgery. A Foley catheter was placed just before surgery and removed the morning after surgery (range 12-22 hours). Prophylactic intravenous antibiotic therapy, cefazoline 2 g and metronidazol 500 mg, was administered during surgery. As this was a new technique the first patients were closely monitored post operatively. No vaginal intercourse was allowed for 6 weeks after the procedure. Each patient was re-assessed at the post-operative consultation 6 weeks after surgery.

Between November 2013 and November 2014, twenty procedures were successfully performed by Poor Man's vNOTES using conventional, reusable laparoscopic instruments. No conversion to standard multi incision laparoscopy or laparotomy was necessary. Fourteen women underwent a unilateral adnexectomy. In six women a bilateral salpingo-oophorectomy was performed.

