1.6. Objectives of the NOTABLE Trial

Is a vNOTES adnexectomy at least as effective compared to the standard transabdominal laparoscopic approach (LSC) for removing a benign adnexal mass without spill?

Secondary research questions are:

- Do more women treated by vNOTES prefer to leave the hospital on the day of surgery compared to LSC?
- Do women treated by vNOTES suffer from less pain compared to women treated by LSC in the first postoperative week?
- Is the removal of a benign adnexal mass by vNOTES faster compared to LSC?
- Does a vNOTES cause more pelvic infection or other complications compared to LSC?
- Does a vNOTES result in more hospital readmissions during the first six weeks following surgery compared to LSC?
- Does a vNOTES approach result in more women reporting dyspareunia, less quality of life or less sexual wellbeing at 3 or 6 months after surgery when compared to women treated by LSC?
- What are the costs of a vNOTES compared to LSC?

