4. TREATMENT ALLOCATIONS

4.1. Surgical procedures

The principal investigator, who has training and experience in both laparoscopy and NOTES, will perform all surgical procedures. He is therefore not blinded. All vNOTES participants will be blinded by three superficial “mock” skin incisions similar to those routinely done with the laparoscopic technique. The wound bandages will be left in place until the day 7 postoperative control to be removed by the coordinating investigator who will state at that moment that the wound healing has left an almost invisible scar as expected. This procedure aims to blind the participants, personnel and outcome assessors. The practice of performing “mock” incisions should not be considered as unethical: it is a procedure that has already been used in some surgical trials to minimise performance and detection bias whenever a subjective outcome is measured (22). The decision to use “mock” surgery is based on the clinical equipoise regarding the balance between benefits and adverse events for the two interventions under comparison (23).

4.1.1 vNOTES adnexectomy

This is the surgical procedure done in the intervention arm of the NOTABLE trial.

Clindamycin vaginal cream is administered on admission of the study participant to the outpatient ward.

The patient is placed in lithotomy position in a vacuum mattress. The abdomen, the vulva and the vagina are disinfected with an alcoholic betadine solution and draped. A Foley catheter is inserted into the bladder.

Three superficial skin incisions are made, one deep in the umbilicus and one in the left and right iliac fossa lateral of the epigastric vessels, and in the suprapubic region. The small vertical intraumbilical skin incision is closed with a monocryl 3/0 intradermal suture. Wound bandages are applied to all three skin incisions.

A 2.5 cm posterior colpotomy is made using a cold knife. The pouch of Douglas is opened using cold scissors. A Gelpoint Mini (Applied Medical) is used as vNOTES port and is inserted into the pouch of Douglas. CO₂ is insufflated until a maximal intraperitoneal pressure of 15mmHg. An optic is inserted and the peritoneal cavity is inspected. The patient is now placed in Trendelenburg position. The small intestine is lifted out of the pelvis.

The ureter is identified, but not routinely dissected. It is only dissected if it cannot be identified transperitoneally. The proximal end of the Fallopian tube is coagulated at its origin into the uterus

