- Postoperative pain defined by the total use of analgesics during the first week following surgery as described in the standardized pain treatment protocol, as an ordinal outcome. The use of pain medication following surgery should be reported in the nursing file. At home the participants should note in their participant log book the name, dosage, route of administration of any analgesic drug that was taken from the moment they are at home until the assessment on day 7 irrespective of whether this was done on their own initiative or after consulting a family physician or any other medical specialist. The assessment of the total use of analgesics will be done on day 7 by the outcome assessor (the coordinating investigator), who is blinded for the intervention done by the principal investigator.
- Postoperative infection defined by lower abdominal pain with fever $> 38^{\circ}\text{C}$ and positive clinical signs or laboratory findings, detected during the first six weeks of surgery, as a dichotomous outcome.
- Per- or postoperative complications according to the Clavien- Dindo classification detected during the first six weeks of surgery, as a dichotomous outcome (Appendix III).
- Hospital readmission during the first six weeks of surgery, as a dichotomous outcome.
- Incidence and intensity of dyspareunia recorded by the participants at 3 and 6 months by self-reporting using a simple questionnaire and VAS scale, as a dichotomous and ordinal

outcome. A measurement of the prevalence and the intensity of dyspareunia will be done at baseline assessment.

- Sexual wellbeing at baseline, at 3 and 6 months by self-reporting the SSFS.
- Quality of life at baseline, at 3 and 6 months by self-reporting the EQ-5D-3L questionnaire.
- Duration of surgery measured as the time in minutes from the insertion of the bladder catheter to the end of vaginal/abdominal wound closure, as a continuous outcome.

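### The clock for duration of surgery starts at bladder catheter insertion, so the blinding-only mock incisions count as vNOTES operating time and bias the comparison against vNOTES

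*Protocol*

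**What the plan says.** Protocol section 5.3 lists operating time as a continuous secondary outcome: "Duration of surgery measured as the time in minutes from the insertion of the bladder catheter to the end of vaginal/abdominal wound closure". It answers one of the secondary questions in section 1.6: "Is the removal of a benign adnexal mass by vNOTES faster compared to LSC".

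Section 4.1.1 sets the order of steps in the vNOTES arm. "A Foley catheter is inserted into the bladder" comes first. Next, "Three superficial skin incisions are made, one deep in the umbilicus and one in the left and right iliac fossa", with a further site named after that. Then: "The small vertical intraumbilical skin incision is closed with a monocryl 3/0 intradermal suture. Wound bandages are applied to all three skin incisions". The posterior colpotomy follows all of this.

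Section 4.1 explains that the mock incisions are given to vNOTES participants only, for blinding, and that the principal investigator performs all the surgery. No part of the Protocol records the mock interval separately or deducts it.

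The team's own case series used another clock (section 1.4.3): "The duration of surgery was defined as the time from the start of colpotomy to the end of vaginal closure".

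**The concern.** An outcome meant to show which technique is quicker should time the techniques. Here one arm's time includes a step that exists only because the trial is blinded and that no vNOTES patient outside the trial would undergo. The other arm has no such step. The error always points the same way, so it can shrink, hide or reverse a true advantage of vNOTES, or create an apparent disadvantage where there is none.

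There is a secondary consequence for costs. Section 5.4 counts staff involvement, overheads and consumables for each procedure. The mock suture and bandages are consumables, and the mock minutes would also be costed if theatre time is used to value staff or overheads. The Protocol does not say that the section 5.3 duration feeds the costing, so this is an inference. The timing problem stands without it.

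**Working it through.** **Step 1. Which steps fall inside the clock (catheter to end of wound closure)?**

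| Step | vNOTES (4.1.1) | Laparoscopy (4.1.2) |
|---|---|---|
| Catheter | clock starts | clock starts |
| Mock incisions | inside | none |
| Suture of umbilical mock incision | inside | none |
| Bandages | inside (before colpotomy) | outside (after closure) |
| Working access | colpotomy, inside | skin incisions, inside |
| Closure of working access | colpotomy closure, clock stops | fascia and skin closure, clock stops |
| Vaginal plug | outside | outside |

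The incisions and skin closure timed in laparoscopy belong to that operation. The only timed work that belongs to neither operation is the mock work, and it occurs only in vNOTES. Only the umbilical mock incision is described as sutured.

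**Step 2. Size of the bias.** Let *m* be the mean time of the mock steps.

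Observed difference (vNOTES minus laparoscopy) = true difference + *m*.

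The Protocol gives no value for *m*, so every value below is an assumption. The reference is the case-series mean of 32 minutes (range 20 to 50; section 1.4.3 and Appendix I). That figure was timed from colpotomy and so contains no mock or preparation time.

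- *m* = 2: 2/32 = 6%
- *m* = 3: 3/32 = 9%
- *m* = 5: 5/32 = 16%
- *m* = 10: 10/32 = 31%

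As a share of the trial's longer interval the figures are lower. Adding the mock time to the denominator gives 2/34 = 6%, 3/35 = 9%, 5/37 = 14% and 10/42 = 24%. Preparation between catheter and first incision would lower them further.

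**Step 3. What this could do to the test (illustration).** The Protocol states no standard deviation, effect size or power for duration, so there is no planned figure to reproduce. Inputs:

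- *n* = 27 per group, the number in section 6.1 before drop-out
- SD = 8 minutes, from the case-series range: (50 − 20)/3.735 = 8.03, where 3.735 is the expected range in SD units for 20 normal observations; and SD = 16 as a doubled, cautious value
- two-sided 5% test, normal approximation, *m* taken as constant
- an assumed true vNOTES advantage of *d* = 8 minutes for the power columns

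Formulas, with SE = SD × √(2/n):

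- P(significant when the true times are equal) = 1 − Φ(1.96 − m/SE) + Φ(−1.96 − m/SE)
- Power to show vNOTES faster = Φ((d − m)/SE − 1.96)

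Worked case with SD 8 and *m* = 5: SE = 8 × √(2/27) = 2.18 and m/SE = 2.30, so the false-significance probability is 63%. Power without the mock time is Φ(8/2.18 − 1.96) = 96%. With it, power is Φ(3/2.18 − 1.96) = 28%.

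| *m* (min) | False significance, SD 8 | False significance, SD 16 | Power, SD 8 (96% if *m* = 0) | Power, SD 16 (45% if *m* = 0) |
|---|---|---|---|---|
| 2 | 15% | 7% | 79% | 28% |
| 5 | 63% | 21% | 28% | 10% |
| 10 | 99.6% | 63% | <1% | <1% |

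**Step 4. Effect of sample size.** With 33 per group (the 66 participants in section 6.1) and *m* = 5, false significance rises from 63% to 72% at SD 8 and from 21% to 25% at SD 16. A larger trial estimates the wrong quantity more precisely.

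**The case against.** The order of steps is not in dispute. The case against the concern is about its weight.

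- **The size is unknown.** The mock times are assumptions, and the 32-minute reference comes from a different clock and from a self-designed port, whereas the trial uses a commercial one. With 2 minutes and SD 16, the error rate rises only from 5% to 7%. This stands: the documents cannot tell a trivial bias from a decisive one. It does not remove the bias, and the missing figure is a reason to record the interval.
- **The direction is conservative for the stated question.** If vNOTES still comes out faster, that conclusion is safe. This also stands, but the advantage would be understated, and a null or slower result could not be read.
- **Catheter insertion is a sensible common start.** It is one identifiable event in both arms, and a colpotomy start cannot be applied to laparoscopy. The case series had no mock incisions, so its different clock is no contradiction. This is fair. It argues for keeping the common start and subtracting the mock interval, not for leaving that interval in.
- **It is one secondary outcome of a pilot trial.** True: the primary outcome, the margin and the sample size are untouched. That limits the severity but does not make the definition right.

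A later analysis plan cannot repair the problem either. If the mock interval is not recorded in theatre, it cannot be recovered.

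**Conclusion.** The concern holds. As written, the section 5.3 definition includes blinding-only work in the vNOTES arm and nothing equivalent in the laparoscopy arm, so the comparison of operating times is biased against vNOTES minute for minute. That conclusion rests only on the order of steps in sections 4.1.1 and 4.1.2 and needs no assumption.

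How much it matters depends on the mock time, which the Protocol does not give. Under assumed mock times of 2 to 10 minutes and SDs of 8 to 16 minutes, the effect runs from slight to enough to decide the answer. The definition should be corrected. It does not threaten the trial's main conclusion.

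**What to change.** Change the definition in section 5.3 in one of two ways:

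1. **Time from the first therapeutic incision.** Start at the colpotomy in vNOTES and at the umbilical incision in laparoscopy, and stop at the end of wound closure in both. This matches the case-series clock for vNOTES. The drawback is that preparation after the catheter is no longer counted, and it may differ between arms.
2. **Keep the catheter start and subtract.** Record the start and end of the mock steps (first mock incision to last bandage), subtract that interval in the vNOTES arm, and report the unadjusted total as a sensitivity analysis. This keeps one common starting event and loses no information.

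In section 5.4, state that time and materials used only for blinding are left out of the procedure costs in either arm.

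The cost is one or two extra time stamps on the theatre record and a change of wording. The time stamps must be in place from the first participant, because the interval cannot be reconstructed afterwards.

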5.4. Health economic outcomes

Costs and consequences of the treatment pathways will be collected from health care providers at the time of the procedure and at follow up in order to conduct the cost-effectiveness analyses.

Resource use data will include:

- Surgical treatment of benign adnexal mass
- Tests and investigations received
- The frequency and duration of out-patient visits and primary care consultations
- Inpatient stays
- Type and volume of medications received
- The number and duration of hospital readmissions and re-treatments.

These data will be collected prospectively from health care providers using a post-operative case report form and patient-completed questionnaires that assess patient health service utilisation at the follow-up time points throughout the trial. Costs incurred by patients will also be collected to conduct an evaluation from a wider societal perspective. Therefore, a patient cost questionnaire will be administered to all trial patients in order to consider the wider cost implications of the interventions which will contain questions to determine out of pocket expenses incurred when attending for treatment and private time costs including time lost from work.

Unit costs obtained from published sources and the trial centre will be used to estimate costs associated with resource use. Responses to the EuroQoL EQ-5D-3L questionnaire will inform the effectiveness in terms of QALYs and clinical effectiveness will be measured in cured cases at six months. We obtained full approval of EUROQoL to use the questionnaire for free.

Data collection will be undertaken prospectively for all trial patients so that a stochastic cost analysis can be undertaken. The process of collecting resource use data will be undertaken separately from data collection on unit costs.

The main resource use to be monitored include the following:

- 1) Consultation time required prior for each procedure for explanation and consent.
- 2) Costs involved with each procedure including level of health care professional involvement in the procedure, equipment required, overheads, consumables and drugs including anaesthesia.

3) Any additional procedures required where initial treatment is unsuccessful or incomplete.

4) Duration of inpatient stay when women opt to stay overnight.

Information on any additional related primary or secondary care contacts will also be collected from all women to ensure any resulting resource use from additional complications is recorded. Unit costs will be obtained and attached to resource items in order that a cost can be calculated for each trial patient. Unit costs will be obtained from published sources and the centre participating in the trial. In addition, the set-up costs of NOTABLE will be estimated and additional analyses will be undertaken including these costs.

5.5. Data management and validation

5.5.1 Confidentiality of personal data

Personal data and sensitive information required for the NOTABLE Trial will be collected directly from participants, who will be informed about the transfer of this information to the trial office at the department of Obstetrics and Gynaecology of the participating centre and will be asked to consent to this. The data will be entered onto a secure computer database, either by staff or directly via a secure internet connection. Any data to be processed outside the trial office will be anonymised. All personal information obtained for the study will be held securely and treated as (strictly) confidential. All staff involved in the NOTABLE Trial (clinical, paramedical, administration) share the same duty of care to prevent unauthorized disclosure of personal information. No data that could be used to identify an individual will be published. We will handle all data confidentially in accordance with the Belgian law of 8 December 1992 on the protection of privacy with respect to the handling of individual personal data.

5.5.2 Long-term storage of data

In line with existing guidelines and Belgian legislation, all data will be stored for up to 15 years after the last participant has reached the 2.5 year follow-up to allow adequate time for review, reappraisal or further research, and to allow any queries or concerns about the data, conduct or conclusions of the study to be resolved.

5.6. Withdrawal from follow-up

Withdrawal from follow-up is the decision of the participant. However, withdrawn patients can bias clinical trial results and reduce the power of the study to detect important differences, so women should be encouraged to complete all follow-up questionnaires. Methods to reduce the burden of follow-up will be explored e.g. online data entry for participants. If the reason for withdrawal is known, it should be communicated to the NOTABLE Trial Office. To reduce loss to follow-up, we shall record patient's social security number, which allows us to track patients changing GP practice. With postal and telephone reminders we anticipate that, the completeness of data should surpass 90% although, as set out below incomplete follow-up is incorporated into the power calculations.

6. ACCRUAL AND ANALYSIS

6.1. Sample size

The sample size for the primary outcome of this trial has been chosen to give good statistical power to preclude any clinically important inferiority of vNOTES compared to laparoscopy and is based on evidence retrieved from a systematic review of the literature (15) and a RCT comparing the excision of mature teratoma using culdotomy with and without laparoscopy (17). An important consideration in adnexal mass surgery is the inadvertent opening of the ovarian capsule. The likelihood of cyst rupture during removal by laparotomy or laparoscopy ranges from 10.5% to 41.8% in published studies (15). Based on a low failure rate to remove dermoid cysts by colpotomy using laparoscopy (2.4%), according to the findings from a RCT (17) we assumed a successful removal of adnexal cysts without spill to be feasible in 95% of all cases. We calculated the sample size with a one-sided test for non-inferiority studies for the primary outcome. The vNOTES approach may be more convenient for women in that no scar in the abdominal wall is required. We believe, therefore, that vNOTES would be the treatment of choice even if 15% less women had successful removal of a benign adnexal mass by using the vNOTES approach. Non inferiority will be concluded when 15% lies above the upper limit of the 95% confidence interval calculated for the difference in the proportion of women successfully treated with either of both techniques. To achieve 80% power to demonstrate non-inferiority under the assumption of similar success rates of 95% in both groups a sample size of 54 participants (27 women per group) will be required. The target sample size was increased to 64 participants (32 women per group) to account for a drop-out rate of 15%.

(<https://www.sealedenvelope.com/power/binary-noninferior/>). Based on the power calculations for the primary outcome, the use of three strata for the randomisation and assuming a loss-to-follow-up rate of 15 % we decided to include 66 study participants in the NOTABLE trial.

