We retrieved a prospective cohort study from the United States (15). This descriptive study was conducted on women treated by a private gynaecological surgery practice in a community hospital setting from January 1, 2004 through April 30, 2011. Two-hundred fifty-seven consecutive women with adnexal masses of 8 cm to 13 cm on preoperative ultrasound examination not meeting triage criteria set forth in ACOG Committee Opinion 280 for referral to gynaecological oncologists were treated with operative laparoscopy, adnexal removal, bagging, and colpotomy. Laparoscopic surgery combined with posterior colpotomy has a low incidence of significant complications. Outcome data show that by observing the principals of minimally invasive surgery, 97% of women were successfully treated as outpatients: 98% of surgeries lasted <136 minutes; 97% had blood loss <200mL, and there were few consequential postoperative complications. Intraoperative rupture of the ovarian capsule was extremely uncommon: capsular rupture was noted in just 1.2% of cases. The most common lesions were cystadenomas, endometriotic cysts and mature teratomas accounting for 85% of all cases. Borderline tumours accounted for 5% of lesions, while invasive ovarian malignancy represented 3.7% of the specimens.

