We retrieved one RCT from Taiwan (17). Seventy-nine women with mature teratomas identified by ultrasound examination and biochemical markers were randomly assigned to have their cysts removed via vaginal cystectomy without laparoscopy (n= 37, group A) or laparoscopic cystectomy via culdotomy (n=42, group B). Inclusion criteria were history of vaginal delivery, no previous abdominal surgery, no history of pelvic inflammatory disease, no medical illness, and no presenting symptoms. Eight women randomised to group A withdrew before surgery. The laparoscopically resected tumours were each put into a cellulose bag, and tumours without laparoscopic- assistance were removed directly via the vagina. Blood loss in group A (88 ± 37 ml) was significantly more than that in group B (64 ± 20 ml, $P= 0.000$). The post-operative recovery times were 20 and 17 hours, respectively ($P= 0.030$). The rates of successful surgery were 58.6 and 97.6%, respectively ($P= 0.002$). The spillage rates were 44.8% and 19.0%, respectively ($P= 0.006$). There were no significant differences in tumour size, patient age, and operative time between groups. The authors concluded that cystectomy without assistance of laparoscopy could be applied to manage mature teratoma of the ovary; however, because of the difficulty of this technique, there were high percentages of tumour spillage and more blood loss during operation and a high percentage of patients who required conversion to laparotomy compared with laparoscopic cystectomy. The authors favour laparoscopically assisted cystectomy to manage mature teratoma.

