5.2. Primary clinical outcome measure

The proportion of women successfully treated by removing the adnexal mass without spill, using a dichotomous outcome measure, will be used as a measure of efficacy. An important consideration in adnexal mass surgery is the inadvertent opening of the ovarian capsule. The likelihood of cyst rupture during removal by laparotomy or laparoscopy ranges from 10.5% to 41.8% in published studies (15). We will consider any spontaneous rupture of the cyst or any need to aspirate the cyst to allow removal from the abdominal cavity as treatment failures, even if the content of the ruptured cyst does not spill freely inside the cavity but remains within the endobag. By avoiding any subjective interpretations this rigorous definition allows an objective measure of success. As the risk of rupture may be associated to the cyst size, due to the stratified random sequence generation we anticipate that the risk of rupture due to the cyst size rather than the technique used will be symmetrically applicable.

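### The 95% spill-free success rate behind the 80% power is derived from a figure for unsuccessful surgery; spillage in the same trial arm was 19.0%.

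*Protocol*

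**What the plan says.** Protocol section 6.1 (Sample size) names two sources, a paper on adnexal masses treated by laparoscopy (reference 15) and an RCT of mature teratoma excision (reference 17). From the first it takes a range: "The likelihood of cyst rupture during removal by laparotomy or laparoscopy ranges from 10.5% to 41.8% in published studies". From the second it takes the figure that leads to the success rate: "Based on a low failure rate to remove dermoid cysts by colpotomy using laparoscopy (2.4"%), from which "we assumed a successful removal of adnexal cysts without spill to be feasible in 95% of all cases". The 80% power with 54 women (27 per group) and a 15-point margin is then stated "under the assumption of similar success rates of 95% in both groups". The target is raised to 64, then 66, for 15% loss.

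Section 1.4.1 summarises the same RCT. Group A had vaginal cystectomy without laparoscopy, and group B (n = 42) had laparoscopic cystectomy via culdotomy. Two separate results are given for A and B in that order: "The rates of successful surgery were 58.6 and 97.6%, respectively" and "The spillage rates were 44.8% and 19.0%, respectively". The same section reports, for the 257-woman cohort in reference 15, that "capsular rupture was noted in just 1.2% of cases".

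Section 5.2 defines the primary outcome as removal without spill and counts "any spontaneous rupture of the cyst or any need to aspirate the cyst to allow removal from the abdominal cavity as treatment failures", even when the contents stay inside the endobag.

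**The concern.** The 2.4% appears to come from the wrong result of the RCT. It describes surgery that did not succeed, whereas the trial's endpoint is removal without spill, rupture or aspiration. The same arm of the same RCT has a spillage figure about eight times as large, and the protocol prints it.

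At a success rate near 95% the binomial variance is small, which is why 27 per group is enough. If the true rate is lower, the variance rises and power falls quickly, even when the two techniques are equally good. Section 6.1 gives no range of power around 95%. A failure to show non-inferiority could then be read as evidence against vNOTES when the trial simply had little chance of success.

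**Working it through.** **1. Which result is the 2.4%?** Section 1.4.1 gives group B 97.6% successful surgery: 100 − 97.6 = 2.4, and 1/42 = 2.38%. Group B spillage is 19.0%: 8/42 = 19.05%. So 34/42 = 80.95% were spill-free, Clopper-Pearson 95% CI 65.9% to 91.4%. (The counts are inferred from the percentages.)

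The two outcomes cannot stand in for each other. With 1 unsuccessful operation and 8 spills, at least 7 of the 8 spills occurred in operations counted as successful. Section 5.2 would count all 8 as failures.

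**2. Do the other cited rates support 95%?**
- Rupture range in 6.1: 100 − 10.5 = 89.5% and 100 − 41.8 = 58.2% rupture-free. The whole range lies below 95%, but it pools laparotomy and laparoscopy.
- Cohort in reference 15: 1.2% of 257 is about 3, so 254/257 = 98.8% were rupture-free, exact 95% CI 96.6% to 99.8%. This is compatible with 95%. Section 6.1 does not use it, and the summary in 1.4.1 does not report aspiration.
- Aspiration: sections 4.1.1 and 4.1.2 provide for it in both arms under stated conditions. No rate is given anywhere in the protocol.

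**3. Reproduce the stated size.** With equal success p in both arms and margin 0.15, the number per group is

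n = (z_alpha + z_power)² × 2p(1 − p) / 0.15².

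At one-sided 5% and 80% power, (1.645 + 0.842)² = 6.183. For p = 0.95, 2p(1 − p) = 0.095, so n = 6.183 × 0.095 / 0.0225 = 26.1, rounded up to 27. Allowing for 15% loss gives 32 per group, 64 in total. The plan's figures are reproduced, so only the input is in question.

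**4. Power at other success rates.** Power = Φ(0.15 / √(2p(1 − p)/n) − 1.645).

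Example at p = 0.81, n = 27: √(0.3078/27) = 0.1068; 0.15/0.1068 = 1.405; Φ(1.405 − 1.645) = Φ(−0.240) = 0.405.

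The evaluable totals are 54 (the calculated size), 56 (66 × 0.85 = 56.1) and 66 (no loss).

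| True success, both arms | 54 | 56 | 66 | Needed per group for 80% |
|---|---|---|---|---|
| 95% | 81% | 82% | 88% | 27 |
| 89.5% | 56% | 57% | 63% | 52 |
| 81% | 41% | 42% | 46% | 85 |

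Exact enumeration with a Wald limit at 27/28/33 per group gives 81/80/85%, 60/59/64% and 42/44/48%, so only whole percentages are meaningful. In the other direction, at 98.8% success the formula gives power above 99%.

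**5. How much slack is there?** By the same formula, 80% power needs success of about 95% with 54 evaluable women (0.948) and about 94% with 66 (0.936).

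**Separate note.** These figures use the one-sided 5% that reproduces 27 per group. Section 6.3 specifies a two-sided 95% interval. With z = 1.960 the powers for 54/56/66 women are 72/73/80% at 95% success, 44/45/51% at 89.5%, and 29/30/34% at 81%. That mismatch is a different point and is not counted here.

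**The case against.** The strongest reply is that 95% may well be right. Section 6.1 opens by naming both sources, and the 257-woman cohort, with adnexal removal, is closer to this trial's procedure than teratoma cystectomy. Its 1.2% rupture rate supports a high success rate. The investigators' own series of 20 vNOTES procedures (section 1.4.3) also lists removal without spillage as a potential benefit. On this view one sentence misreads one source, and the low power figures rest on rates that may not apply here: 81% comes from cystectomy, and 89.5% is the favourable end of a pooled range. Loss should also be small, because section 5.1.2 measures the primary outcome at the end of surgery, so a number near 66 is more natural than 54.

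Much of this stands. The evidence does not refute 95%, and 81% and 89.5% are sensitivity values. The evaluable number should be read as a range: early measurement argues for little loss, while section 3.1 leaves the final eligibility decision to surgery and 6.1 itself allows 15%.

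The reply does not restore the derivation. Section 6.1 ties the 95% to the 2.4% and does not use the 1.2%. The cohort summary does not report aspiration, and the case series gives no spill count. The objection that cystectomy differs from adnexectomy applies equally to the 2.4%, which comes from the same arm as the 19.0%. Pilot status does not remove the point either, because the protocol sets a formal margin and a power target.

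**Conclusion.** The point holds and should be fixed. The 2.4% in section 6.1 is a rate of unsuccessful surgery, not of spill, and the protocol's own summary gives 19.0% spillage in the same arm. The 95% that supports the 80% power therefore has no valid stated basis, although it has not been shown to be false.

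If both techniques truly succeed in 89.5% of women, power is 56% to 63%; at 81% it is 41% to 46%, against 81% to 88% at the assumed 95%. These figures assume equal true success in both arms, the 15-point margin, the calculation's one-sided 5%, a normal approximation (Wald limit), and 54 to 66 evaluable women. The main unknown is how often aspiration will be needed, and no passage of the protocol gives that rate.

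**What to change.** Change section 6.1 only.

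1. Remove the 2.4% as the ground for spill-free success.
2. Give a basis that matches the section 5.2 outcome (spill, rupture or aspiration), or state that no cited source reports it. Set the 19.0% spillage (teratoma cystectomy) beside the 1.2% capsular rupture (adnexal removal, aspiration not reported), each with its limitation.
3. Beside the 80% at 95% success, state the power of the planned size at, for example, 95%, 89.5% and 81%, for 54 to 66 evaluable women, in whole percentages. Note separately that power is lower under the two-sided 95% interval of section 6.3.
4. State that if success is below 95%, a failure to show non-inferiority may reflect low power.

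The cost is a few sentences and a less favourable account of power. No patients or procedures are added, and the sample size and margin do not change.
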